## **7.9 Outcomes Research**

### **7.9.1 FACT-G**

Descriptive statistics (mean, standard deviation, median, first and third quartiles, minimum, maximum) will be calculated for the difference from baseline for each item at each period. These analyses will be based on all treated subjects who have a baseline measurement and an on-study assessment for the time-point of interest. Summary statistics on the difference from baseline over time will be prepared for each scale.

### **7.9.2 FKSI-19**

Descriptive summary statistics of the FKSI-19 total score and each subscale score (Disease Related Symptoms-Physical (DRS-P), Disease Related Symptoms-Emotional (DRS-E), Treatment Side Effects (TSE), Function/Well-Being (FWB)) will be presented at baseline and each on-study time

point. Mean changes from baseline for each of the outcome assessments will be calculated for each participant at each on-study time point.

The questionnaire completion rate for the FKSI-19, defined as the proportion of questionnaires received out of the expected number (i.e., the number of subjects still on study), will be calculated and summarized at each assessment time point. Missing data will not be imputed for the analyses.

A by-subject listing of FKSI-19 question score, total score, and each sub scale score will be provided.

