[REDACTED]		[REDACTED]
[REDACTED]		[REDACTED]
[REDACTED]		[REDACTED]
[REDACTED]		[REDACTED]
Efficacy Assessment		
Tumor Assessment	See Notes	
FIRST tumor assessment should be performed at 12 weeks (\pm 1 week) following randomization (until disease progression or treatment discontinuation, whichever occurs later).
 
Contrast enhanced CT Chest, CT (or MRI with and without contrast) abdomen, pelvis and all known sites of disease. Use same imaging method as was used at screening/baseline.
 
Participants with a history of brain metastasis should have surveillance MRI (with and without gadolinium approximately every 12 weeks, or sooner if clinically indicated (until disease progression or treatment discontinuation, whichever occurs later)

Table 2-2: On-Study Assessments Part 1 (CA209800)

Procedure	For Part 1, Study treatment Every 3 Weeks for 4 Doses (Both Arm A and Arm B)	Notes
	Cycle 1, 2, 3, 4 (Day 1)	
Outcomes Research Assessments		
FACT-G, EQ-5D-3L, and FKSI-19	X	To be completed at the start of the clinic visit every 6 weeks. First questionnaire should be completed after randomization but before dosing. (Cycle 1, 3)
Health Care Utilization	X	Health Care Utilization will be collected at each visit
Clinical Drug Supplies		
IRT Drug Vial Assignment	X	Within 24 hours prior to dosing
Administer Study Treatment	X	First dose to be administered within 72 hours following randomization.

Table 2-3: On-Study Assessments - Part 2 (CA209800)

Procedure	For Part 2, Study treatment is Administered Every 4 Weeks (Both Arm A and Arm B)	Notes Cycle 5 will begin 6 weeks after Cycle 4
	Cycle 5 and beyond (Day 1)	
Safety Assessments		
Targeted Physical Examination	X	To be performed only if clinically indicated within 72 hours prior to dosing
Vital Signs	X	Including BP, HR, and temperature within 72 hours prior to dosing
Physical Measurements (including performance status)	X	Weight and KPS within 72 hours prior to dosing
Adverse Events Assessment	Continuously	
Review of Concomitant Medications	X	

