Laboratory Tests	X	Beginning at Cycle 5 and every alternate dose thereafter (Cycle 7, 9, 11, 13, etc.), on-study local laboratory assessments should be done within 72 hours prior to dosing and include: CBC w/differential, LFTs (ALT, AST, total bilirubin, alkaline phosphatase), BUN or serum urea level, creatinine, corrected Ca, Na, K, Cl, LDH, glucose, amylase, lipase, phosphate, TSH with reflexive Free T4, Free T3. Beginning at Cycle 6 and every alternate dose thereafter (Cycle 8, 10, 12, 14, etc.), on-study local laboratory assessment should be done within 72 hours prior to dosing and include: LFTs (ALT, AST, total bilirubin, alkaline phosphatase) and creatinine.
Pregnancy Test (WOCBP only)	X	Serum or urine (minimum sensitivity equivalent units 25IU/L or equivalent units of HCG) every 4 weeks. A negative pregnancy test should be documented within 24 hours prior to start of each dose of investigational product.
Outcomes Research Assessments		
FACT-G, EQ-5D-3L, and FKSI-19	X	To be completed at the start of the clinic visit every 4 weeks from Cycle 5 onwards
Health Care Utilization	X	Health Care Utilization will be collected at each visit from Cycle 5 onwards

Table 2-3: On-Study Assessments - Part 2 (CA209800)

Procedure	For Part 2, Study treatment is Administered Every 4 Weeks (Both Arm A and Arm B)	Notes Cycle 5 will begin 6 weeks after Cycle 4
	Cycle 5 and beyond (Day 1)	
Pharmacokinetic and Immunogenicity Assessments		
Immunogenicity blood sample	X	Refer to Table 9.5-1
PK Samples	X	Refer to Table 9.5-1
Efficacy Assessment		
Tumor Assessment	See Notes	
First tumor assessment during Part 2 should occur after 8 weeks (\pm 1 week) relative to previous tumor assessment performed at Week 12.
 
Subsequent tumor assessments should occur every 8 weeks (\pm 1 week) for the first 12 months from randomization.
 
From the second year from randomization, tumor assessments should occur every 12 weeks (\pm 2 weeks) until disease progression or treatment discontinuation, whichever occurs later.
 
Contrast enhanced CT Chest, CT (or MRI with and without contrast) abdomen, pelvis and all known sites of disease. Use same imaging method as was used at screening/baseline.
 
Participants with a history of brain metastasis should have surveillance MRI brain with and without gadolinium approximately every 12 weeks, or sooner if clinically indicated (until disease progression or treatment discontinuation, whichever occurs later).

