Clinical Drug Supplies		
IRT Drug Vial Assignment	X	
Administer Study Treatment	X	Note: Within 72 hours from vial assignment, the participant must receive the dose of study medication.

Table 2-4: Follow-up Assessments (CA209800)

Procedure	Follow Up, ^a Visits X1 and X2	Survival, ^b Follow-up Y Visits	Notes
Safety Assessments			
Targeted Physical Examination	X		To assess for potential late emergent study treatment related issues
Adverse Event Assessments	X	X	
Laboratory Tests	X		On site/local CBC w/differential, LFTs, BUN, creatinine, amylase, lipase and TSH (+ reflex Free T4 and Free T3) for X1, repeat at X2 if study treatment related toxicity persists.
Pregnancy Test (WOCBP Only)	X		Serum or urine
Review of Concomitant Medications	X		
Pharmacokinetic Samples and Immunogenicity Assessments			
PK Samples	X		Refer to Table 9.5-1
Immunogenicity blood sample	X		Refer to Table 9.5-1
Survival Status			
Participant Status	X	X	Every 3 months, Survival Follow up Visits may be accomplished by visit or phone contact, to include subsequent anti-cancer therapy
Efficacy Assessments			
Tumor Assessments	See Notes		
Only for participants without progression on study therapy. SUBSEQUENT tumor assessments should continue to occur every 8 weeks (\pm 1 week) thereafter for the first 12 months, then every 12 weeks (\pm 2 weeks) until disease progression or treatment discontinuation, whichever occurs later.
 
Contrast enhanced CT Chest, CT (or MRI with and without contrast) abdomen, pelvis and all known sites of disease. Use same imaging method as was used at screening/baseline.
 
Participants with a history of brain metastasis should have surveillance MRI

Table 2-4: Follow-up Assessments (CA209800)

Procedure	Follow Up, ^a Visits X1 and X2	Survival, ^b Follow-up Y Visits	Notes
			Brain without and with gadolinium approximately every 12 weeks, or sooner if clinically indicated (until disease progression or treatment discontinuation, whichever occurs later).
Outcomes Research Assessments			
FACT-G and FKSI-19	X		Collection done at X1 and X2 only
EQ-5D-3L	X	X	Collection done during X1 and X2. Survival follow-up every 3 months for the first year and 6 months thereafter
Health Care Utilization	X		Collection done at X1 and X2 only
████████████████████			
██████████	█	█	██

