10.3.2.4 Outcomes Research Analyses

Descriptive summary statistics of Quality of life (QoL) assessments will be presented at baseline and each on-study time point, unless otherwise specified. Mean changes from baseline for each of the three scales will be calculated for each subject at each on-study time point. In addition, subject compliance will be described per time point by the proportion of subjects who filled out the QoL assessments over the numbers of subject known to be alive and eligible for assessment at these time points.

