### **7.5.2 Progression Free Survival**

PFS curves for each treatment group will be estimated using the Kaplan-Meier (KM) product limit method in All Treated Subjects. Median PFS and corresponding two-sided, 95% confidence intervals will be computed. Descriptive HRs and corresponding two sided 95% CIs for Arm A relative to Arm B will be estimated using a Cox proportional hazards model, with treatment group as a single covariate, stratified by IMDC prognostic score at screening (IVRS source). PFS rates at 6 months with 95% CIs will be estimated using KM methodology.

The source of progression event (death versus progression) will be summarized by treatment group.

The status of subjects who are censored in the PFS KM analysis will be tabulated for each treatment group using the following categories:

- On-study (on-treatment, in follow-up)
- Off-study (lost to follow-up, withdrawn consent, never treated)
- Received subsequent anticancer therapy

[REDACTED]

Survival rates at 6 months will be estimated using KM estimates on the OS curve for each treatment group. Associated two-sided 95% CIs will be calculated.

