### **7.9.3 EuroQol EQ-5D**

Unless otherwise specified, the analysis of EQ-5D will be performed in all treated subjects who have an assessment at baseline and at least one or more post-baseline assessments.

Subject's overall health state on a visual analog scale (EQ-VAS) and change from baseline in EQ-VAS at each assessment time point will be summarized by treatment group using descriptive statistics (N, mean, SD, median, 25th and 75th percentiles, minimum, maximum). A plot summarizing the mean change from baseline in EQ-VAS will be presented

Proportion of subjects reporting problems for the 5 EQ-5D dimensions at each assessment time point will be summarized by level of problem and by treatment group. Percentages will be based on number subjects assessed at assessment time point.

EQ-5D questionnaire completion rate, defined as the proportion of questionnaires actually received out of the expected number (ie, number of subjects on treatment or in follow up), will be calculated and summarized for each assessment time point by treatment group.

EQ-5D Index values will be computed using a scoring algorithm based on the UK MVH-A1 TTO value set. Change from baseline in EQ-5D Index score at each assessment time point will be summarized by treatment group using descriptive statistics (N, mean, SD, median, 25th and 75th percentiles, minimum, maximum). A plot summarizing the mean change from baseline in EQ-5D Index score will be presented

A by-subject listing of EQ-5D with the problem levels for each of the 5 dimensions (mobility, self-care, usual activities, pain/discomfort and anxiety/depression), health state (5 dimensions digits combined in a 5-digit number) and EQ-VAS will be provided.

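### SAP 7.9.2 counts everyone still on study as expected to return an FKSI-19 form at each time point, so completion at dosing cycles falls as participants stop treatment even when no due form is missed

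*SAP*

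**What the plan says.** **Denominators**

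- SAP 7.9.2: the FKSI-19 completion rate, summarised at each assessment time point, is "defined as the proportion of questionnaires received out of the expected number (i.e., the number of subjects still on study".
- SAP 7.9.3: the EQ-5D completion rate counts forms received "out of the expected number (ie, number of subjects on treatment or in follow up".
- Protocol 10.3.2.4: compliance at each time point is the proportion who filled out the assessment "over the numbers of subject known to be alive and eligible for assessment at these time points".
- SAP 7.5.2, listing the status of participants censored for PFS, has the category "On-study (on-treatment, in follow-up".

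**When the forms are due (Protocol Section 2)**

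- Table 2-2, Part 1, all three questionnaires: "To be completed at the start of the clinic visit every 6 weeks", with Cycles 1 and 3 named.
- Table 2-3, Part 2, all three: "To be completed at the start of the clinic visit every 4 weeks from Cycle 5 onwards".
- Table 2-4, after treatment, FACT-G and FKSI-19: "Collection done at X1 and X2 only". The survival-visit column is blank.
- Table 2-4, after treatment, EQ-5D: X1 and X2, then "Survival follow-up every 3 months for the first year and 6 months thereafter".

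Protocol 8.1 and 8.1.1 keep participants in the study after they stop treatment. The synopsis puts survival follow-up at about 5 years.

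**The concern.** A completion rate should answer one question: of the forms that were due, how many came back? The denominator in SAP 7.9.2 does not depend on whether a form was due. A participant who stops treatment after Cycle 3 has no Cycle 5, 7 or 9 visit, and has no FKSI-19 form at all after X2, but remains on study and so in the denominator. The reported rate then mixes two different things: stopping treatment and failing to return a form.

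SAP 7.9.2 does not impute missing FKSI-19 data, so a reader will look at completion to judge how selected the group behind each mean score is. A low figure could be taken for poor compliance when it only reflects discontinuation. The protocol and the SAP would also give different numbers for the same quantity.

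**Working it through.** The documents state no completion rate, compliance target or discontinuation rate, so there is no planned figure to reproduce. The discontinuation shares below are assumptions.

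**Step 1. Rates at a dosing-cycle time point when every due form is returned.** Let T be the number on treatment and F the number off treatment but still in follow-up. Forms due = forms received = T.

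- SAP 7.9.2 rate = T / (T + F)
- Protocol 10.3.2.4 rate = T / T = 100%

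**Step 2. Illustration with 100 treated participants (the target in SAP Section 5).**

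| Off treatment (assumed) | SAP rate, all of them in follow-up | SAP rate, half of them dead or off study | Protocol rate |
|---|---|---|---|
| 20 | 80/100 = 80.0% | 80/(80+10) = 88.9% | 100% |
| 40 | 60/100 = 60.0% | 60/(60+20) = 75.0% | 100% |
| 60 | 40/100 = 40.0% | 40/(40+30) = 57.1% | 100% |

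**Step 3. Movement over cycles.** Cycle 4 falls 9 weeks after the first dose, Cycle 5 six weeks later at week 15, and cycles then run every 4 weeks. Cycle 9 is therefore at week 31, or 31 × 7 / 30.4375 = 7.13 months. Assume exponential time on treatment with median m months, and death independent of stopping. The share of living participants still on treatment is then 2^(−7.13/m): about 29%, 54% or 70% for m = 4, 8 or 14. These would be the SAP rates at Cycle 9 with perfect return.

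**Step 4. Would X1 and X2 forms fill the gap?** X1 is 30 days after the last dose and X2 is 84 days after X1, so X2 falls about 114 days (3.75 months) after the last dose. Suppose, generously, that everyone within 114 days of the last dose is credited with a form at Cycle 9. The rate becomes 2^(−(7.13−3.75)/m): about 56%, 75% or 85%. The shortfall shrinks but remains.

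**Step 5. X1 and X2.** Here the error has a different source. Suppose 40 of 100 have stopped, all have reached X1 and returned the form, and 60 are still on treatment. The literal SAP rate is 40/(40+60) = 40%, against 40/40 = 100% of forms due. It rises, not falls, as participants stop treatment and return the form.

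**Step 6. EQ-5D.** Participants in follow-up do owe EQ-5D forms, at X1, X2 and survival visits. Read literally, SAP 7.9.3 counts all of them at dosing cycles too, and Steps 1 and 2 apply. Read visit by visit (those on treatment at cycles, those in follow-up at follow-up visits), most of the distortion goes. The SAP does not say which is meant.

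**The case against.** **On study may mean on treatment.** The category in SAP 7.5.2 belongs to a PFS censoring table and is not a SAP-wide definition. Protocol Tables 2-2 and 2-3 are titled as on-study assessments, while Table 2-4 is titled as follow-up. If SAP 7.9.2 means still in the treatment schedule, the dosing-cycle denominator is right. But this reading rests on table titles. It conflicts with SAP 7.5.2 and with Protocol 8.1, under which participants who stop treatment remain in the study, and it would leave nobody expected at X1 or X2, where FKSI-19 is due.

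**Expected may already imply due.** A participant with no Cycle 9 visit is not ordinarily expected at Cycle 9. For FKSI-19, however, the SAP spells out what the expected number is. For EQ-5D the argument has force, and the visit-by-visit reading is reasonable.

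**The Data Presentation Plan may settle it.** SAP Section 9 refers to that plan for table layouts, and it was not available for this review. It may set workable denominators, but the SAP should not state a different rule.

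**The consequence is small.** This stands. The tables are descriptive, the SAP presents no p-values, EQ-5D dimension percentages use the number assessed, and by-subject listings are planned.

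**Stronger readings the documents do not support**

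- A reader might infer that EQ-5D has the same definite fault. Its follow-up schedule and the ambiguous wording do not allow that.
- A reader might infer that completion falls at every time point. The fall applies to dosing cycles only.
- A reader might infer a false compliance gap between arms. That needs unequal discontinuation, for which the documents give no figure.
- A reader might infer that the plan makes completion its yardstick for trusting the quality-of-life results. No passage says so; Protocol 10.3.2.4 only says compliance will be described.

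**Conclusion.** The point holds for FKSI-19. Followed as written, SAP 7.9.2 gives a dosing-cycle completion rate below 100% whenever anyone is off treatment and in follow-up, even with every due form returned. It also gives too low a rate at X1 and X2 while anyone is still on treatment. It departs from Protocol 10.3.2.4 by dropping the condition that the participant be eligible at that time point. For EQ-5D the finding is only that SAP 7.9.3 needs clarifying.

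That the rate is understated follows from the wording and the schedule. Its size does not: the range of 40% to 88.9% in Step 2 depends on assumed discontinuation of 20% to 60% and on how many of those participants have died or left. The effect is confined to descriptive questionnaire-completion tables. Questionnaire scores and the primary and secondary endpoints are unaffected.

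**What to change.** In SAP 7.9.2 and 7.9.3, define the expected number at each time point as treated subjects who are alive, have not withdrawn, and are scheduled for that questionnaire at that time point under Protocol Tables 2-2 to 2-4:

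- Cycles 1, 3 and 5 onward: participants on treatment and at that cycle.
- X1 and X2: participants who have reached that visit.
- Survival follow-up: EQ-5D only, at the 3-monthly and later 6-monthly collections.

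This matches Protocol 10.3.2.4. If availability of data among all participants is also of interest, show the number still on study in a separate column. The cost is SAP wording and table programming; no new data are needed.

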### **7.9.3 EuroQol EQ-5D**

Unless otherwise specified, the analysis of EQ-5D will be performed in all treated subjects who have an assessment at baseline and at least one or more post-baseline assessments.

Subject's overall health state on a visual analog scale (EQ-VAS) and change from baseline in EQ-VAS at each assessment time point will be summarized by treatment group using descriptive statistics (N, mean, SD, median, 25th and 75th percentiles, minimum, maximum). A plot summarizing the mean change from baseline in EQ-VAS will be presented

Proportion of subjects reporting problems for the 5 EQ-5D dimensions at each assessment time point will be summarized by level of problem and by treatment group. Percentages will be based on number subjects assessed at assessment time point.

EQ-5D questionnaire completion rate, defined as the proportion of questionnaires actually received out of the expected number (ie, number of subjects on treatment or in follow up), will be calculated and summarized for each assessment time point by treatment group.

EQ-5D Index values will be computed using a scoring algorithm based on the UK MVH-A1 TTO value set. Change from baseline in EQ-5D Index score at each assessment time point will be summarized by treatment group using descriptive statistics (N, mean, SD, median, 25th and 75th percentiles, minimum, maximum). A plot summarizing the mean change from baseline in EQ-5D Index score will be presented

A by-subject listing of EQ-5D with the problem levels for each of the 5 dimensions (mobility, self-care, usual activities, pain/discomfort and anxiety/depression), health state (5 dimensions digits combined in a 5-digit number) and EQ-VAS will be provided.

## **8 CONVENTIONS**

See Core Safety SAP.

For death dates, the following conventions will be used for imputing partial dates:

- If only the day of the month is missing, the 1st of the month will be used to replace the missing day. The imputed date will be compared to the last known date alive and the maximum will be considered as the death date.
- If the month or the year is missing, the death date will be imputed as the last known date alive.

- If the date is completely missing but the reason for death is present the death date will be imputed as the last known date alive.

For date of progression, the following conventions will be used for imputing partial dates:

- If only the day of the month is missing, the 1st of the month will be used to replace the missing day\*.
- If the day and month are missing or a date is completely missing, it will be considered as missing.

\*In cases where the date of death is present and complete, the imputed progression date will be compared to the date of death. The minimum of the imputed progression date and date of death will be considered as the date of progression.

For other partial/missing dates not covered by Core Safety SAP, the following conventions may be used:

- If only the day of the month is missing, the 15th of the month will be used to replace the missing day.
- If both the day and the month are missing, “July 1” will be used to replace the missing information.
- If a date is completely missing, it will be considered as missing.

The following conversion factors will be used to convert days to months or years:

1 month = 30.4375 days and 1 year = 365.25 days

Duration (e.g. time from first diagnosis to first dosing date, duration of response, and time to response) will be calculated as follows:

$$\text{Duration} = (\text{Last date} - \text{first date} + 1)$$

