8.3 Lost to Follow-Up

- All reasonable efforts must be made to locate participants to determine and report their ongoing status. This includes follow-up with persons authorized by the participant.
- Lost to follow-up is defined by the inability to reach the participant after a minimum of **three** documented phone calls, faxes, or emails as well as lack of response by participant to one registered mail letter. All attempts should be documented in the participant's medical records.
- If it is determined that the participant has died, the site will use permissible local methods to obtain date and cause of death.
- If investigator's use of third-party representative to assist in the follow-up portion of the study has been included in the participant's informed consent, then the investigator may use a Sponsor retained third-party representative to assist site staff with obtaining participant's contact information or other public vital status data necessary to complete the follow-up portion of the study.
- The site staff and representative will consult publicly available sources, such as public health registries and databases, in order to obtain updated contact information.
- If after all attempts, the participant remains lost to follow-up, then the last known alive date as determined by the investigator should be reported and documented in the participant's medical records.

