#### **4.2.6 Progression Free Survival**

[figure not shown]
The sixth secondary endpoint is PFS. PFS is defined as the time from the date of randomization to the first date of documented progression, as determined by the investigator per RECIST 1.1, or death due to any cause, whichever occurs first. Clinical deterioration in the absence of progression per RECIST 1.1 is not considered progression for the purpose of determining PFS. Subjects who die without a reported progression will be considered to have progressed on the date of their death. Subjects who did not progress or die will be censored on the date of their last evaluable tumor assessment. Subjects who did not have any on study tumor assessments and did not die will be censored on their date of randomization. Subjects who started any subsequent anti-cancer therapy, including tumor directed radiotherapy, tumor directed surgery, or systematic anticancer therapy, without a prior reported progression will be censored on the date of their last evaluable tumor assessment prior to the initiation of the subsequent anti-cancer therapy.

The progression free survival rate at time T is defined as the probability that a subject has not progressed and is alive at time T following randomization.

Further explanation for various censoring scenarios for the definition of PFS are presented in [Figure 4.2.7-1](#)

Figure 4.2.7-1: Graphic Display of PFS Definition

[Redacted text block]

[REDACTED]

[REDACTED]

[REDACTED]

[REDACTED]

[REDACTED]

[REDACTED]

[REDACTED]

[REDACTED]

[REDACTED]

[REDACTED]

[REDACTED]

[REDACTED]

[REDACTED]

[REDACTED]

[REDACTED]

[REDACTED]

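### SAP 8 dates a death with no recorded month at last contact even when the recorded year is later, and leaves PFS status undefined for a progression known only by year

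*SAP*

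**What the plan says.** SAP 8 (Conventions) has three sets of rules for incomplete dates.

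- **Death, only the day missing.** The first of the month is imputed, and then: "The imputed date will be compared to the last known date alive and the maximum will be considered as the death date".
- **Death, month or year missing.** "If the month or the year is missing, the death date will be imputed as the last known date alive". No comparison with any recorded year follows.
- **Progression, only the day missing.** The first of the month is imputed. A footnote to this rule caps the result at a complete death date.
- **Progression, day and month missing.** "If the day and month are missing or a date is completely missing, it will be considered as missing". The footnote is not attached to this rule.
- **Other dates not covered by the Core Safety SAP.** "If both the day and the month are missing, “July 1” will be used to replace the missing information". The recorded year is kept.

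These dates feed PFS. SAP 4.2.6 runs PFS from randomization "to the first date of documented progression, as determined by the investigator per RECIST 1.1, or death due to any cause, whichever occurs first". Its censoring sentence reads: "Subjects who did not progress or die will be censored on the date of their last evaluable tumor assessment". Its death sentence reads: "Subjects who die without a reported progression will be considered to have progressed on the date of their death".

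For participants who are lost to follow-up, Protocol 8.3 allows a third party to help obtain "other public vital status data necessary to complete the follow-up portion of the study".

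**The concern.** The two death rules stand next to each other and follow different logic. With the month known, the SAP never dates a death before what the record allows. With only the year known, it drops that safeguard, and the analysis date can fall in a calendar year that the record rules out. The error has one direction: the death is always too early. It enters OS, which Protocol 8.1.1 treats as a key endpoint, and PFS for anyone who dies without a reported progression.

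For progression the gap is of a different kind. The year is thrown away and the event has no usable date, but no visible sentence says what then happens to the participant in the PFS analysis. If the program falls back on censoring at the last evaluable assessment, the participant is censored because of progression. That is informative censoring and pushes PFS upward.

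The section keeps the year for miscellaneous dates and discards it for these two, which carry more weight.

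**Working it through.** The plan gives no figure for these rules, so there is none to reproduce. The check applies the rules to assumed dates and then estimates the effect of a lost progression.

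**Deaths.** Let L be the last known alive date and Y the recorded year of death, with the month unknown. The SAP date is L. The earliest date that fits the record is the later of L and 1 January of Y. So:

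- provable error = max(0, 1 January Y − L)
- largest possible error = 31 December Y − L

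| L (assumed) | Y | SAP date | Provable error (days) | Largest possible error (days) |
|---|---|---|---|---|
| 2 Oct 2017 | 2018 | 2 Oct 2017 | 91 | 455 |
| 15 Nov 2017 | 2018 | 15 Nov 2017 | 47 | 411 |
| 20 Dec 2017 | 2018 | 20 Dec 2017 | 12 | 376 |
| any date in 2018 | 2018 | L | 0 | at most 364 |

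The last row matters. When last contact falls in the recorded year, the SAP rule and a later-of-two-dates rule give the same answer.

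Protocol Table 2-4 sets survival contacts every 3 months. With the SAP's own conversion, 3 × 30.4375 = 91.3 days. If those contacts are kept, the participant died within about 91 days of L, so the error cannot exceed about 91 days. For a participant lost to follow-up no such limit applies. With L = 1 July 2018 and Y = 2020, the provable error is 184 + 365 = 549 days, or 549 / 30.4375 = 18.0 months.

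**Progressions: which PFS sentence applies?** Take a participant with a documented RECIST progression and a date known only to the year.

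- The event definition needs a first date of progression, and SAP 8 has set that date to missing.
- The censoring sentence covers those who neither progressed nor died. This participant progressed.
- The death sentence covers deaths without a reported progression. This participant has one, although the general definition still names death as an event.

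No sentence fits, so PFS status is undefined in the visible text.

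**Size if such participants were censored.** Assumptions: 50 treated per arm (SAP 5); exponential PFS with medians of 6, 9 and 12 months; administrative censoring uniform between 9 and 15 months (6 months of accrual and 9 months of minimum follow-up, from the SAP's Schedule of Analyses); the lost progressions occur before 6 months; each is censored 8 weeks earlier, one scan interval. The medians and the number of lost events are not in the documents. Mean change in one arm's 6-month Kaplan-Meier PFS, in percentage points, from 1,500 simulated arms per cell:

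| Assumed median PFS | 1 lost | 2 lost | 3 lost |
|---|---|---|---|
| 6 months | +1.2 | +2.4 | +3.7 |
| 9 months | +1.4 | +2.9 | +4.4 |
| 12 months | +1.6 | +3.2 | +4.8 |

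As a plausibility check, one event in 50 is 1/50 = 2.0 points. Removing it cannot raise the 6-month rate by more than that, because Kaplan-Meier passes part of the censored participant's weight to others who progress before 6 months.

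**The case against.** **The cases should be rare.** PFS counts only investigator RECIST 1.1 progression, taken from scheduled scans, and SAP 4.2.6 excludes clinical deterioration. A progression known only by year would need a scan with no known month. This stands, and it is why the progression point is secondary.

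**Year-only deaths are not shown to occur.** Protocol 8.3 permits public sources, but nowhere says that they yield only a year, and it expects sites to obtain the date of death. This also stands. The route is plausible, and its frequency is unknown.

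**The SAP may deal with it elsewhere.** SAP 4.2.6 refers further censoring scenarios to Figure 4.2.7-1, and SAP 8 refers to the Core Safety SAP. Neither is visible here. This could settle the progression half. It does not repair the death rule, which SAP 8 states explicitly.

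**The consequence is small.** SAP 7.1 plans no formal testing and no p-values, the rules are the same in both arms, and the primary endpoint is a safety rate. All true. They limit the weight of the point and do not make the death date right.

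Three stronger readings are tempting, and the documents do not support them. A reader might infer that a documented progression becomes a non-event for PFS. The SAP does not say so; its censoring sentence excludes a participant who progressed, and a later death might still be counted. A reader might infer that the best-response window stays open. SAP 4.2.5 lets all response designations count only for participants without documented progression, so that too is unstated. And a reader might infer that every death with a missing month is misdated against the record. The first table shows a provable error only when the recorded year is later than the year of last contact.

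**Conclusion.** The death half holds as a stated rule that gives a wrong date. When the month is missing and the recorded year is later than the year of last contact, SAP 8 places the death in a year that the record contradicts. The death is still counted; only its timing is wrong, and always too early. The provable error is 12 to 91 days in the three late-2017 examples, at most about 91 days if 3-monthly contacts are kept, and potentially far longer after loss to follow-up. The 18-month example needs a long gap in contact and would probably matter only to survival analyses after the planned final analysis, expected about 15 months from the start of randomization.

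The progression half holds in a narrower form: the recorded year is discarded and PFS status is left undefined in the visible text. Censoring is a likely programmed result. If it happened, PFS would be biased upward by the amounts in the second table, which rest on assumed medians and assumed numbers of lost events.

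Both affect rare cases in descriptive analyses of OS and PFS. The primary safety endpoint is untouched. This is a low-cost correction to make before database lock, and it does not threaten the trial's main conclusion.

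**What to change.** Change two rules in SAP 8.

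1. **Death, year known and month missing:** use the later of 1 January of the recorded year and the last known alive date. This extends the existing day-missing rule. In the 15 November 2017 example the date moves to 1 January 2018, which removes the provable 47 days. Up to 411 − 47 = 364 days of real uncertainty remain, as any year-only date implies. Keep the current rule for a missing year.
2. **Progression, year known and month missing:** state that a documented progression remains a PFS event. Bound its date below by the later of 1 January of the recorded year and the last progression-free assessment, and above by the earlier of 31 December of that year and death. Name in advance which point in that interval is used, and say that the same date closes the best-response window.

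If Figure 4.2.7-1 or the Core Safety SAP already covers the second case, a cross-reference is enough. The cost is two sentences and minor programming, with no new data. Because the trial is open-label, settling this before database lock also avoids case-by-case decisions with the arm known.
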